10.3.1.8 Serious adverse event exemptions

In general, SAEs are defined according to ICH Topic E2A (CPMP/ICH/377/95), EU Directive 2001/20/EC and ENTR/CT-3 (see Section 10.3.1.4). In the present trial, some events are excluded from the SAE definition. The following events do not need to be reported as SAEs:

- SAEs occurring later than the SFU2 visit (see Section 1.3) must only be reported by the investigator to the sponsor if a relationship to trial treatment or trial procedure is suspected.
- Hospitalizations for respite care will not be considered as reportable SAE.
- Hospitalizations solely for coordination of care, including hospice arrangements, will not be considered as reportable SAE.
- Hospitalizations that were necessary solely because of patient requirement for outpatient care outside of normal outpatient clinic operating hours will not be considered as reportable SAE.
- Planned hospitalizations required by the protocol (e.g., for trial treatment administration or insertion of access device for trial treatment administration) will not be considered as reportable SAE.
- Hospitalization of a patient for monitoring and symptomatic treatment for up to 24 h due to a transient inflammatory reaction of Grade 1 or 2 will not be considered as an SAE (but needs to be documented as AE).
- Hospitalizations for procedures or interventions of a pre-existing condition of the
 patient (elective surgery = planned, non-emergency surgical procedure) will not
 be considered as a reportable SAE (unless the intervention/procedure is not
 caused by an acute worsening of the pre-existing condition during the time trial
 participation).
- if it was planned and documented in patient record before the trial-specific patient informed consent was signed (ICF for trial participation, see Section 10.1.3, or
- if it was scheduled during the trial when elective surgery became necessary and the patient has not experienced an AE.

Nevertheless, this kind of hospitalization should be avoided during trial treatment.

- The progression of underlying disease (e.g., new metastases) during trial
 participation is not considered as AE. However, specific symptoms at time of
 progression that may be caused by other reason, and fatal cases where other
 reason rather than the PD may not be discarded, have to be documented as
 AEs and reported as SAEs if applicable.
- Routine treatment or monitoring of the underlying disease not associated with any deterioration in the patient's condition.

Page 111 of 133 Version: 7.0 Date: 09 FEB 2023

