10.3.1.1 Events meeting the AE definition

Any abnormal laboratory test results (hematology, clinical chemistry, or urinalysis) or other safety assessments (e.g., ECG, radiological scans, vital signs measurements), including those that worsen from baseline, considered clinically significant in the medical and scientific judgment of the investigator.

Exacerbation of a chronic or intermittent pre-existing condition including either an increase in frequency and/or intensity of the condition.

New conditions or worsening of pre-existing conditions detected or diagnosed after signing ICF.

Signs, symptoms, or the clinical sequelae of a suspected drug-drug interaction.

Signs, symptoms, or the clinical sequelae of a suspected overdose of either trial treatment or a concomitant medication. Overdose per se will not be reported as an AE/SAE.

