10.3.1.4 Definition of a serious adverse event

If an event is not an AE per definition above, then it cannot be an SAE even if serious conditions are met (e.g., hospitalization for signs/symptoms of the disease under trial).

An SAE is defined as any untoward medical occurrence that, at any dose:

- · Results in death
- Is life-threatening

The term "life-threatening" in the definition of "serious" refers to an event in which the patient was at risk of death at the time of the event. It does not refer to an event, which hypothetically might have caused death, if it were more severe.

- Requires inpatient hospitalization or prolongation of existing hospitalization
 - In general, hospitalization signifies that the patient has been detained (usually involving at least an overnight stay) at the hospital or emergency ward for observation and/or treatment that would not have been appropriate in the physician's office or outpatient setting. Complications that occur during hospitalization are AEs. If a complication prolongs hospitalization or fulfills any other serious criteria, the event is serious. When in doubt as to whether "hospitalization" occurred or was necessary, the AE should be considered serious.
 - Hospitalization for elective treatment of a pre-existing condition that did not worsen from baseline is not considered an AE.
- Results in persistent disability/incapacity
 - The term disability means a substantial disruption of a person's ability to conduct normal life functions.
 - This definition is not intended to include experiences of relatively minor medical significance such as uncomplicated headache, nausea, vomiting, diarrhea, influenza, and accidental trauma (e.g., sprained ankle) which may interfere with or prevent everyday life functions but do not constitute a substantial disruption.
- Is a congenital anomaly/birth defect.

Page 105 of 133 Version: 7.0 Date: 09 FEB 2023

Other situations:

- Medical or scientific judgment should be exercised in deciding whether SAE reporting is appropriate in other situations such as important medical events that may not be immediately life-threatening or result in death or hospitalization but may jeopardize the patient or may require medical or surgical treatment to prevent one of the other outcomes listed in the above definition. These events should usually be considered serious.

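### A stray second *not* in Protocol 10.3.1.8 inverts the SAE exemption for procedures on a pre-existing condition

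*Protocol*

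**What the plan says.** Protocol 10.3.1.8 states that some events are taken out of the SAE definition in this trial and introduces its list with "The following events do not need to be reported as SAEs". One entry begins "Hospitalizations for procedures or interventions of a pre-existing condition of the" patient. A bracketed gloss limits it to elective surgery, meaning surgery that is planned and not an emergency. These admissions are not to "be considered as a reportable SAE (unless the intervention/procedure is not", and the clause then names the cause to which its last word applies: "caused by an acute worsening of the pre-existing condition during the time trial".

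The sentence closes there. Two fragments follow, joined by *or*:

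- "if it was planned and documented in patient record before the trial-specific patient informed consent was signed"
- "if it was scheduled during the trial when elective surgery became necessary and the patient has not experienced an AE"

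Two other sections deal with the same situation. Section 10.3.1.4, to which 10.3.1.8 refers for the SAE definition, says: "Hospitalization for elective treatment of a pre-existing condition that did not worsen from baseline is not considered an AE". Section 10.3.1.1 lists among the events that are AEs: "Exacerbation of a chronic or intermittent pre-existing condition including either an increase in frequency and/or intensity of the condition".

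**The concern.** The entry grants an exemption and then states an exception to it. The exception should name the cases that must be reported after all, which are procedures made necessary because the condition got worse. The second *not* makes it name the opposite cases.

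Sites consult this list when deciding not to file an SAE form, so it is an operative rule. Because it is presented as a trial-specific carve-out, a site could read it as overriding the general definition. An admission wrongly treated as exempt would be missing from 24-hour reporting (Protocol 10.3.1.10), from the assessment for expedited reporting, from the safety data that the IDMC receives, and from the serious-event tables in SAP 8.5.2. The opposite mistake would put routine elective admissions into those tables.

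**Working it through.** No arithmetic applies. The check is logical.

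**Step 1: the sentence alone.** Let W mean that an acute worsening during the trial caused the procedure. As printed, the rule is: not reportable, unless not W.

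| Rule | W true | W false |
|---|---|---|
| 10.3.1.8 as printed | exception does not apply; stays exempt | exception applies; exemption lost |
| 10.3.1.1, 10.3.1.4 and 10.3.1.10 together | an AE; serious if it requires inpatient admission; report within 24 h | elective treatment without worsening is not an AE, so it cannot be an SAE |
| 10.3.1.8 with the second *not* deleted | exception applies; exemption lost, so reportable | stays exempt |

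The printed row is the reverse of the second row in both columns. The corrected row agrees with it in both. Strictly, losing an exemption is not the same as a duty to report, but a site would naturally take it that way.

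**Step 2: the neighbouring rules.** Section 10.3.1.2 leaves out fluctuations of existing disease only if they do not worsen. The last entry of 10.3.1.8 exempts routine care of the underlying disease only when the patient has not deteriorated. In both rules, as in 10.3.1.4, worsening removes the exemption. Only the clause at issue uses worsening to keep it.

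**Step 3: the two conditions.** The effect of the error depends on whether they belong to this entry.

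If they do belong, with the sentence as printed:

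- *W true, planned before consent.* A procedure planned that early is, by its timing, rarely one caused by a worsening during the trial. What remains is an operation already planned and then carried out because the condition acutely worsened. That case is exempt as printed. It should be rare, because exclusion criterion 13 in Protocol 5.1.2 bars patients who have surgery planned during participation.
- *W true, scheduled during the trial.* The worsening is an AE under 10.3.1.1, so the requirement of no AE fails and the admission is not exempt.
- *W false, either condition met.* The conditions grant an exemption that the parenthesis takes away.

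On this reading the entry exempts almost nothing, which cannot be its purpose. With the second *not* deleted, the conditions fit: elective procedures without worsening are exempt, as in 10.3.1.4.

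If the conditions do not belong to the entry, nothing limits the inversion for elective procedures brought on by worsening. The sentence ends before the fragments, so the text leaves this open, although the list layout may have been lost when the PDF was read.

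**The case against.** The strongest reply is that nobody would be misled. The intended rule is stated correctly in 10.3.1.4, exacerbation is an AE under 10.3.1.1, and 10.3.1.10 requires every SAE in the observation period to be reported. A site would have to prefer one garbled parenthesis to three clear rules. The entry is confined to planned, non-emergency surgery, and the two conditions stop most worsening-driven admissions from being exempted. On this account the practical result is over-reporting of elective admissions, which is a nuisance and does not hide a safety signal.

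Much of this stands. The scope is narrow, the intent can be recovered, and under-reporting is limited if the conditions are read as attached. The worsening would also still be an AE under 10.3.1.1, so even a literal reader of 10.3.1.8 should record it. What would be lost is its serious status and the 24-hour report.

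The reply does not rescue the sentence. The protocol gives contradictory instructions for the same admission, the conditions make sense only once the second *not* is gone, and over-reporting is also an error in the serious-event tables.

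**Conclusion.** The sentence is wrong as written and contradicts Sections 10.3.1.1, 10.3.1.4 and 10.3.1.10. It is a drafting error of minor severity. The documents give no count of elective procedures for pre-existing conditions, so its size cannot be calculated. The judgement that it is small assumes that the bracketed gloss defines the scope and that most sites would read the two conditions as part of the entry.

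Three stronger readings are tempting but not supported:

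- *That every admission due to a worsening condition is exempt.* The entry covers only procedures or interventions, glossed as elective surgery.
- *That autoimmune flares under cemiplimab would go unreported.* Such a flare would ordinarily lead to a medical admission, which is outside this entry. Protocol 8.4 sends cemiplimab-related immune events of Grade 3 or higher to the sponsor within 24 hours on the SAE form, serious or not. Protocol 5.1.2 excludes significant autoimmune disease within the last 5 years that required systemic immunosuppression.
- *That one missed SAE could decide the enrollment pause at 4 of the first 10 Arm 1 patients.* Under Protocol 7.4, related Grade 3 to 5 events count as triggers without having to be serious, apart from the listed exceptions. That review also appears to be past: Protocol 2.3.1 and 2.3.4 (version 7.0) refer to interim safety data, IDMC recommendations to continue without modification, and enrolment of about 50% of the originally planned patients.

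**What to change.** Delete the second *not* in the parenthesis, so that the exception applies when the procedure is "caused by an acute worsening of the pre-existing condition during the time trial" participation. Indent the two conditions under this entry and word them as conditions of the exemption, so that the whole agrees with 10.3.1.4. Tell sites about the corrected wording.

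The cost is one word, a change of list layout and a short site memo. No analysis, sample size, dose or eligibility rule changes. Because version 7.0 has been in use, a quick look at admissions recorded against non-serious AEs would show whether any site followed the clause literally. This check is optional.

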8.3 Adverse events and serious adverse events

The investigator and any qualified designees are responsible for detecting, documenting, and recording events that meet the definition of an AE or SAE and remain responsible for following up all AEs and SAEs.

8.3.1 Time period and frequency for collecting adverse event and serious adverse event information

All AEs and SAEs will be collected from the first signing of the ICF until the SFU2 visit (90 days after last trial dose or until a new anti-cancer therapy is started) at the time points specified in the SoA (Section 1.3). Additionally, in case a new anti-cancer therapy is started within 90 days after last treatment, the safety follow-up visit should be performed just prior to starting the new anti-cancer therapy. Adverse events after start of new anti-cancer therapy do not need to be reported unless a causal relationship to BNT111-01 or cemiplimab is suspected.

All SAEs (initial and follow-up reports) will be recorded and reported to the sponsor or designee within the appropriate time frame and under no circumstance should this exceed 24 h after knowledge of the event, as indicated in Section 10.3.1.10. AESIs should also be reported within an appropriate time frame (i.e., no more than 24 h after knowledge of the event).

Investigators are not obligated to actively seek AEs or SAEs after a patient has discontinued from the trial. However, if the investigator learns of any SAE, including a death, at any time after a patient has discontinued from the trial, and he/she considers the event to be reasonably related to the trial treatment or trial participation, the investigator must promptly notify the sponsor.

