8.3.6 Death events

Any death that occurs within the observation period (from the first signing of the ICF until 90 d after the last trial dose) will be reported as an SAE. A copy of an autopsy report should be submitted if available upon request. Date and cause of death will be recorded.

In case of a fatal event, the event term should not be "death" but the underlying event which led to death (death = outcome). If there is more than one AE in a fatal case, only for the AE leading to death the outcome "fatal" should be selected. If the cause of death is unknown and cannot be ascertained at the time of reporting, the most likely reason for death should be documented as event term.

Deaths due to disease progression occurring within 90 days of the last trial treatment must be reported as a Grade 5 SAE. The AE term on the SAE form should be reported as "disease progression" of the disease under trial treatment, i.e., "progression of advanced/metastatic melanoma". All deaths due to disease progression occurring after 90 days from the end of trial treatment will be reported on the trial-specific death page of the eCRF.

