8.3.7 Disease-related events and/or disease-related outcomes not qualifying as AEs or SAEs

Non-fatal events that are clearly consistent with the expected pattern of progression of the underlying disease (e.g., new metastases) should **not** be recorded as AEs. These data will be captured as efficacy assessment data only and will be recorded on the tumor response evaluation pages in the eCRF. In most cases, the expected pattern of progression will be based on RECIST 1.1. In rare cases, the determination of clinical progression will be

Page 85 of 133 Version: 7.0 Date: 09 FEB 2023

based on symptomatic deterioration; however, every effort should be made to document progression using objective criteria.

If there is any uncertainty as to whether an event is due to disease progression, it should be reported as an AE.

Note: Symptoms resulting from the progression and clearly stated as related to the PD will not be documented as AEs nor reported as SAEs. However, specific symptoms at time of progression that may be caused by other reason and death due to disease progression, will have to be documented as AEs and reported as SAEs if applicable.

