10.3.1.2 Events not meeting the AE definition

Any clinically significant abnormal laboratory findings or other abnormal safety assessments which are associated with the underlying disease, unless judged by the investigator to be more severe than expected for the patient's condition.

The disease/disorder being studied or expected progression, signs, or symptoms of the disease/disorder being studied, unless more severe than expected for the patient's condition.

Exceptions: All deaths due to disease progression occurring within 90 days of the last trial treatment must be reported as SAEs. Specific symptoms at time of progression that may be caused by other reason (unrelated to progression) have to be documented as AEs and reported as SAEs, if applicable.

Medical or surgical procedure (e.g., endoscopy, appendectomy): the condition that leads to the procedure is the AE.

Situations in which an untoward medical occurrence did not occur (social and/or convenience admission to a hospital).

Anticipated day-to-day fluctuations of pre-existing disease(s) or condition(s) present or detected at the start of the trial that do not worsen.

Page 104 of 133 Version: 7.0 Date: 09 FEB 2023

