In addition, treatment-related TESAEs for both randomized and add-on treatment will be summarized by PT nested within SOC for BNT111 and cemiplimab separately.

Related Serious Adverse Events by NCI-CTCAE grade

The number and percentage of patients with related TESAEs (for BNT111 and cemiplimab separately and related to both the treatments) will be summarized by worst NCI-CTCAE grade by PT nested within SOC. Worst grade will be counted if a TEAE is reported more than once by the same patient for a SOC / PT

Deaths

All deaths including those that occurred on-treatment (deaths occurred between first
and last trial treatment intake during the study + 30 days) and post-treatment (deaths
occurred after the last trial treatment intake during the study + 30 days), will be listed.
Post treatment deaths will be flagged. In addition to the summary of on-treatment
deaths and post-treatment deaths, an additional summary of all deaths (on-treatment
+ post-treatment) will be provided along with primary reason for death.

Page 49 of 78 Version: Final v7.0 Date: 05Mar2024

- A separate summary of TESAEs leading to death will be provided by PT nested within SOC.
- A separate summary of related TESAEs leading to death (for BNT111 and cemiplimab separately and related to both the treatments) will be provided by PT nested within SOC.

AE listings

All TEAEs, fatal AEs, SAEs, TEAEs leading to dose reduction and interruption, TEAEs leading to permanent discontinuation of treatment, Infusion-related reactions, irAEs, and TEAEs related to trial procedures will be listed.

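### Protocol sections disagree on whether a death clearly due to melanoma progression, or a death after new anti-cancer therapy, within 90 days of last dose is an SAE, so the fatal-TESAE count depends on which section a site follows

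*Protocol*

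**What the plan says.** **Sections that make a progression death reportable.** Protocol 8.3.6 sets its own window: "Any death that occurs within the observation period (from the first signing of the ICF until 90 d after the last trial dose" counts as an SAE. For progression deaths within 90 days of last treatment it also fixes the grade and the reported term: they must "be reported as a Grade 5 SAE. The AE term on the SAE form should be reported as" disease progression. Section 10.3.1.2 states the general rule that expected progression is not an AE and then carves out fatal cases: "Exceptions: All deaths due to disease progression occurring within 90 days of the last trial treatment" must be reported as SAEs. Section 8.3.7 is softer. It says "death due to disease progression, will have to be documented as AEs and reported as SAEs if applicable", with no 90-day window and no grade.

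**Section that points the other way.** Section 10.3.1.8 lists events that need not be reported as SAEs. One bullet says that progression of the underlying disease is not an AE. The only fatal cases it brings back are those where some other "reason rather than the PD may not be discarded, have to be documented as" AEs. It has no 90-day clause and no reference to 8.3.6 or 10.3.1.2.

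**Start of a new therapy.** Section 8.3.1 collects AEs and SAEs to 90 days after last dose or until a new anti-cancer therapy starts, and adds: "Adverse events after start of new anti-cancer therapy do not need to be reported unless a causal relationship to BNT111-01 or cemiplimab is suspected". SOA1 footnote c and SOA2 footnote b say the same. Section 10.3.1.10, the SAE reporting instruction, refers to 8.3.1 for the period of observation.

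**Analysis.** SAP 8.5.2 counts patients with any TESAE, any Grade ≥3 TEAE and any TESAE leading to death. It adds: "A separate summary of TESAEs leading to death will be provided by PT nested within" SOC.

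**The concern.** A site deciding whether to file an SAE form would naturally look in the section headed as SAE exemptions. Read as written, that section tells the site not to file for a patient who has plainly died of melanoma. The section on deaths tells the same site that it must file. The new-therapy rule creates a second split, and it applies to death from any cause: a patient who starts another treatment on day 40 and dies on day 60 is outside the 8.3.1 window and inside the 8.3.6 window.

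Fatal TEAEs by relationship are part of a stated secondary safety endpoint, and SAP 5.1 sends the outputs of SAP 8.5.2 to every regular IDMC meeting. These tables are built from the AE and SAE records that sites file. If sites apply different sections, the pooled fatal, any-serious and Grade ≥3 rows partly reflect reporting practice. The SAP cannot recover a form that was never filed.

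**Working it through.** The plan gives no figure to reproduce, so the check is a comparison of the passages, followed by the size of one affected death.

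**Case 1. Death clearly due to progression on day 60 after last dose, no new therapy.**

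| Section | Result |
|---|---|
| 8.3.6 | SAE, Grade 5, termed disease progression |
| 10.3.1.2 | SAE, by express exception |
| 8.3.7 | AE, and SAE where applicable |
| 10.3.1.8 | No report, since progression is not an AE and no other cause is in play |

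The last row is by implication. No sentence in 10.3.1.8 says outright that progression deaths are exempt. But restoring only the cases with a possible other cause would serve no purpose if all progression deaths were reportable anyway.

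**Case 2. New anti-cancer therapy on day 40, death on day 60, no suspected link to trial treatment.**

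| Section | Result |
|---|---|
| 8.3.6 | SAE: "until 90 d after the last trial dose) will be reported as an SAE", with no new-therapy limit |
| 8.3.1, SOA1 footnote c, SOA2 footnote b | No report required |
| 10.3.1.10 | Report if within the observation period, which it takes from 8.3.1 |

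**Which outputs change.** Under Protocol 10.3.1 and SAP 8.5.2, causality is required for treatment-emergent status only when onset is more than 90 days after last dose. A reported progression death within 90 days therefore enters the TESAE tables whatever its cause.

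- Fatal TESAE: the patient counts as 1 if the form is filed and 0 if not.
- Any TESAE and Grade ≥3 TEAE: these count patients, so the figure changes only if the patient had no other qualifying event.

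**Size per death.** Planned arm sizes in the SAP trial-design table (section 3.3) are 90, 45 and 45. Assuming that all randomized patients are treated as assigned, so that the safety set equals the randomized set:

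- Arm 1: 1/90 = 1.1 percentage points.
- Each monotherapy arm: 1/45 = 2.2 percentage points.

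For k affected deaths the shift in the fatal-TESAE rate is k/90 or k/45. The documents give no early death rate, so k is left open.

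**Which outputs do not change.**

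- Overall survival and the SAP summary of all deaths with primary reason rest on recorded dates and causes of death, not on SAE status.
- The table of related TESAEs leading to death: a suspected causal link makes the event reportable under every section above.
- The early Grade 5 enrollment-pause trigger in Protocol 7.4 excludes events clearly unrelated to study drug, with underlying disease as its example, so it is largely protected.

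**The case against.** The best defence is that the text mostly settles the matter itself. The 10.3.1.8 bullet gives new metastases as its example of progression. Section 8.3.7 uses the same example and limits it to non-fatal events. The mandatory rule for deaths appears in both 8.3.6 and 10.3.1.2, and a specific rule stated twice would normally prevail over a general exclusion. Section 10.3.1.4, under which something that is not an AE cannot be an SAE, does not help the opposite reading, because it refers back to an AE definition that includes the progression-death exception. This shows that 10.3.1.8 is the outlier and what the sponsor probably intended. It does not remove the conflict: the exemption list has no cross-reference, and its restriction on fatal cases is at odds with the other sections. Nor does it touch the new-therapy conflict, where the reporting instruction itself points to the shorter window.

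A reader might go further in three ways that the documents do not support.

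- *That the SAP cannot separate progression deaths from other fatal events.* SAP 8.5.2 tabulates fatal TESAEs by preferred term, and 8.3.6 fixes the term for progression deaths, so those reported should be identifiable. Related fatal TESAEs are shown separately, as are all deaths with primary reason.
- *That a drug-related death could be hidden.* A fatal case with a possible other cause is reportable even under 10.3.1.8, and causality is assessed for every AE. Misattributed cause of death is a different problem, which neither section creates.
- *That a particular number of deaths will be lost.* This needs an early progression-death rate, and for Case 2 a rate of switching therapy. The documents give neither. Progressors in Arms 2 and 3 may also continue on add-on treatment, which moves the last-dose date.

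**Conclusion.** The concern holds as a conflict between reporting rules in current protocol text. Section 10.3.1.8 exempts by implication a death that 8.3.6 and 10.3.1.2 make mandatory to report, and 8.3.1 with its footnotes closes a window that 8.3.6 keeps open to day 90. Following 10.3.1.8 or 8.3.1 as written leads a site to omit reports that 8.3.6 requires.

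The damage is confined to the fatal-TESAE, any-TESAE and Grade ≥3 TEAE counts. It is 1.1 points per affected death in Arm 1 and 2.2 points in a monotherapy arm for the fatal count, and at most that for the other two. These figures assume planned arm sizes with every randomized patient treated. The total effect depends on how many such deaths occur and which section each site follows, neither of which is in the documents. The primary endpoint is untouched, and no formal comparison between arms is planned. The point merits correction because the rule is wrong as written and the remedy is cheap. It does not threaten the trial's main conclusions.

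**What to change.** 1. **Protocol 10.3.1.8.** Limit the progression bullet to non-fatal progression, and refer to 8.3.6 and 10.3.1.2 for every death up to 90 days after last treatment.
2. **Protocol 8.3.1, SOA1 footnote c and SOA2 footnote b.** State whether deaths up to day 90 are reported once a new anti-cancer therapy has started, in line with 8.3.6, so that the reference in 10.3.1.10 leads to the same window.
3. **SAP 8.5.2, optional.** Add one row to the overall AE summary for TESAEs leading to death excluding events coded as progression of the disease under study. The table by preferred term already shows these events separately, so this only makes the headline row easier to read.

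The cost is a few sentences of protocol text, some additional SAE forms from sites that had applied the exemption or the new-therapy cut-off, and one table row if the third item is taken up.
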